8 DATA ANALYSIS PLANS

8.1 In principle, the following items will be summarized and analyzed

(1) Matters concerning the disposition of patients

- Number of patients enrolled and number of patients whose case report forms (CRFs) are completed
- Numbers of patients analyzed for safety and efficacy
- Number of patients excluded from analysis and reasons for exclusion
- Date of withdrawal/dropout and their reasons

(2) Matters concerning safety

- Occurrence of AEs (e.g., types, severity and incidence of AEs)
- Occurrence of adverse drug reactions (ADRs) (e.g., types, severity and incidence of ADRs)

(3) Matters concerning efficacy

- Change in the volume of ovarian chocolate cyst (If there are two or more cysts, a total volume)

- Change over time in dysmenorrhea score (total of a dysmenorrhea severity score and a score for the use of analgesics)
- Change over time in VAS for dysmenorrhea
- Change in serum CA125

8.2 Analysis Methods

Statistical analyses are outsourced to Densuke Systems Co., Ltd.

Appropriate statistical procedures will be used according to the characteristics of the endpoint set.

**Post Marketing Observational Study
Statistical and Analytical Plans**

(DUPKST16002)

**A SURVEY ON EFFICACY AND SAFETY IN PATIENTS
WITH ENDOMETRIOSIS**

Ver. 1.0

Changes in the Statistical Analysis Plan

Version 1.0 of the statistical analysis plan was finalized on September 15, 2017. No revisions were made to the plan thereafter.

Table of contents

1	Introduction	4
2	Outline of the Study.....	4
3	List Of Abbreviations And Definition Of Terms.....	4
4	Organization for Statistical Analysis Activities	4
5	Study Design.....	5
5.1	Study Schedule	5
5.2	Outcome measures	6
5.3	Determination of Sample Size.....	6
6	Handling of Data	6
6.1	Analysis Set.....	6
6.2	Handling of Data by Period.....	6
6.3	Handling of Data to Derive Variables.....	7
6.4	Handling of Adverse Event Data.....	7
7	Matters concerning statistical analysis	7
7.1	Level of Significance for Statistical Testing and Confidence Level for Interval Estimation.....	7
7.2	Software to be Used for Statistical Analysis	7
7.3	Statistical Methods	7
8	Statistical Analysis Variables	8
8.1	Disposition of Subjects	8
8.2	Patient Characteristics	8
8.3	Efficacy Variables.....	9
8.3.1	Study Primary Variables	9
8.3.2	Study Secondary Variables	9
8.4	Safety Variables	10
8.4.1	Adverse Events	10

1 Introduction

This document provides details of the statistical analysis plan for the “Post Marketing Observational Study of Duphaston Tablets 5 mg - a Survey on Efficacy and Safety in Patients with Endometriosis” (hereinafter referred to as the “study”). The purpose of the statistical analysis plan is to ensure that data are analyzed properly and efficiently as planned.

2 Outline of the Study

Duphaston tablets have been available for the treatment of endometriosis in Japan since 1965. This study is designed to collect efficacy and safety data in patients with endometriosis to obtain information for the effective and safe use of Duphaston tablets.

Clinical Supply	Duphaston® 5 mg Tablets
Title (Protocol Number)	Post Marketing Observational Study A SURVEY ON EFFICACY AND SAFETY IN PATIENTS WITH ENDOMETRIOSIS (DUPKST16002)
Study Design	Prospective, non-intervention, non-blind, non-control observational study
Observation period	4 cycles
Planned sample size	65 subjects

3 List Of Abbreviations And Definition Of Terms

Term/abbreviation	Definition
The summary statistics	Number of subjects, mean, standard deviation, minimum, median, and maximum

4 Organization for Statistical Analysis Activities

DENSUKE SYSTEMS Co., Ltd. will be contracted by Mylan EPD G.K. to perform the statistical analysis activities planned in this document.

Details of the organization are provided in the “Statistical Analysis Procedure.”

5 Study Design

5.1 Study Schedule

Registration Form/Case Report Form	Registration Form	Case Report Form					
		At enrollment	Before treatment initiation	At treatment initiation (cycle 1)	Cycle 2	Cycle 3	Cycle 4
Registration information							
(1) Subject identification No.	○						
(2) Subject initials	○						
(3) Birth date or age	○						
(4) Planned start date of treatment	○						
(5) Oral consent	○						
Patient background characteristics							
(1) Diagnosis		○					
(2) Body height and weight		○					
(3) Pregnancy and lactation status		○					
(4) Menstruation and ovulation status		○					
(5) Complications		○					
(6) Past history		○					
(7) History of allergy		○					
(8) Serious hepatopathy or liver disease		○					
(9) Heart or kidney disease		○					
(10) History of drug treatment		○					
(11) History of surgical treatment		○					
Treatment compliance, clinical course and efficacy							
(1) Observation date (date of confirmation)		○	○		○		○
(2) Start date of treatment		○					
(3) Compliance with Duphaston treatment			○	⊙	○	⊙	○
(4) Measurement of ovarian chocolate cyst		○			○		○
(5) Severity of dysmenorrhea		○	○	⊙	○	⊙	○
(6) Use of analgesics		○	○	⊙	○	⊙	○
(7) VAS for dysmenorrhea		○	○	⊙	○	⊙	○
(8) Concomitant medications/therapies		○	○	⊙	○	⊙	○
(9) Date of withdrawal/dropout and its reason							○
Laboratory tests							
(1) Serum CA125		●					●
(2) Others						Δ	
Adverse events							
Adverse events					○		

One cycle will consist of one menstruation cycle.

Each endpoint will be observed in cycles marked with a symbol. Observation results should be entered in the EDC system.

○: Endpoint

⊙: Investigate information on the next observation day, and enter it.

●: Perform the test during a non-menstruation period.

Δ: Enter information if observed.

5.2 Outcome measures

【Efficacy Variables】

- The volume measurements of ovarian chocolate cysts
- Dysmenorrhea severity
- The use of analgesics
- Dysmenorrhea score
- VAS for dysmenorrhea
- Serum CA125

【Safety Variables】

- Adverse events

5.3 Determination of Sample Size

Planned sample size of the survey: 65 subjects

Rationale for setting:

Whether or not the size of chocolate cyst of the ovary reduced at the end of treatment from baseline will be evaluated using the sign test. When anticipated results would be a decrease-increase ratio of 7:3 and 10% of all subjects being unchanged, a sample size is calculated to be 58 subjects. Assuming a dropout rate of 10%, a necessary sample size of the survey is 65 subjects.

6 Handling of Data

6.1 Analysis Set

The analysis set will consist of all subjects who satisfy inclusion and exclusion criteria and are enrolled in this survey.

The efficacy evaluation will be summarized in the “efficacy analysis set,” which consists of all subjects who receive Duphaston and for whom any of the efficacy variables are observed. The evaluation will also be summarized in the “study completers,” which consists of subjects who complete the treatment without discontinuation.

The safety evaluation will be summarized in the “safety analysis set,” which consists of all subjects who receive the drug.

6.2 Handling of Data by Period

Since the observation period will be set based not on the number of days from the start date of administration but on the menstruation cycle, and the observation data in each menstrual cycle will be obtained from investigation of status per cycle without identifying the first day of menstruation as a base point, the cycles entered in the EDC system will be used as they are and each item will be summarized according to the applicable observation schedule, namely before the start of treatment (cycle -1), at the start of treatment (cycle 1), cycle 2, cycle 3, cycle 4 and at the completion of the observation period (cycle 5). The last observation of the actual evaluations after cycle 1 including those at discontinuation (except for “unknown”) will be summarized as “at last observation.”

Since the recommended regimen of this survey is to start the dosage on the fifth day of each menstrual cycle, the administration can be started during menstruation of cycle 1.

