4.1.2 Exclusion Criteria

Subjects corresponding to those who are listed in the CONTRAINDICATIONS or PRECAUTIONS Sections for Duphaston[®] Tablets as well as patients meeting the following exclusion criteria will not be included in the subjects of the survey.

- (1) Subjects who used GnRH agonists within 6 months before patient enrollment
- (2) Subjects who utilized hormone preparations containing corpus luteum hormone or estrogen as an active ingredient, low-dose contraceptive pills, middle-dose contraceptive pills, testosterone derivatives, or herbal products indicated for endometriosis within 3 months before patient enrollment
- (3) Subjects who received surgical treatment for endometriosis such as transvaginal alcohol fixation, laparotomy or laparoscopic surgery within 2 months before patient enrollment
- (4) Subjects who are pregnant or may possibly be pregnant at patient enrollment
- (5) Subjects who are in breast feeding at patient enrollment
- (6) Subjects who are determined by the investigator/subinvestigator to be not suitable for the subjects of the survey because of other reasons

[CONTRAINDICATIONS]

- (1) Subjects with serious liver disorder or liver disease
- (2) Subjects with known hypersensitivity to the active substance or to any of the excipients
- (3) Subjects with known or suspected progestogen dependent neoplasms (e.g. meningioma)
- (4) Subjects with undiagnosed vaginal bleeding

[PRECAUTIONS]

Careful Administration

- (1) Subjects with a past or current history of heart or kidney disease
- (2) Subjects with liver disorder
- (3) Subjects with porphyria
- (4) Subjects with depression
- (5) Subjects with abnormal liver function values caused by acute or chronic liver disease
- (6) Subjects with rare hereditary problems of galactose intolerance, Lapp lactase deficiency or glucosegalactose malabsorption

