- For a chocolate cyst of the ovary newly confirmed during the treatment period, whether it is a cyst that has not been accidentally measured before treatment initiation or a new cyst will be inputted in the column for comments.
- For a chocolate cyst of the ovary that becomes difficult to identify during the treatment period, such a fact and its number will be entered in the column for comments.

(v) Severity of dysmenorrhea (dysmenorrhea severity score)

- The severity of dysmenorrhea will be assessed in accordance with Table 2, and a score will be entered. A dysmenorrhea score²⁾ will be calculated using a total of the recorded score and a score for the use of analgesics.

(vi) Use of analgesics (including over-the-counter drugs) for the treatment of dysmenorrhea (score for the use of analgesics)

- The use of analgesics will be assessed in accordance with Table 3, and a score will be entered. A dysmenorrhea score will be calculated using a total of the recorded score and a dysmenorrhea severity score.

(vii) Visual analogue scale (VAS) for dysmenorrhea

- The VAS for dysmenorrhea will be assessed in accordance with Table 4. A length (cm) from the left end of the line (0) will be measured. Measured values (cm) will be rounded off to one decimal place and inputted.

[figure not shown]
Table 2 Severity of dysmenorrhea

Severity of dysmenorrhea	Contents	Score
None	None	0
Mild	Rarely interfering with work (study and house work)	1
Moderate	Interfering with work (study and house work) requiring lying down to rest	2
Severe	Being confined to bed for ≥ 1 day, being unable to work (study and house work)	3

Table 3 Use of analgesics

Use of analgesics	Contents	Score
None	None	0
Mild	An analgesic was used for a day during the last (or current) menstruation period.	1
Moderate	An analgesic was used for 2 days during the last (or current) menstruation period.	2
Severe	An analgesic was used for ≥ 3 days during the last (or current) menstruation period.	3

Table 4 VAS for dysmenorrhea

(viii) Concomitant medications/therapies (If “yes,” the name of a drug, daily dose, route of administration, reason for administration, start date of administration, end date of administration, name of concomitant therapy, reason for implementing concomitant therapy, start date of concomitant therapy, and end date of concomitant therapy will be inputted.)

(ix) Date of withdrawal/dropout and its reason

(3) Laboratory tests

(i) Serum CA125

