7.1 Level of Significance for Statistical Testing and Confidence Level for Interval Estimation

Unless otherwise specified, statistical testing will be performed with a two-sided level of significance of 5%, and a two-sided confidence level of 95% will be used for interval estimation. No multiplicity adjustment will be made.

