8.3.1 Study Primary Variables

(1) Change in the volume of ovarian chocolate cyst before and after treatment

For the volume calculated from the major and minor axes of ovarian chocolate cyst, the values before treatment initiation and at last observation will be compared, frequency of increase and decrease will be summarized and the sign test will be performed separately in the “efficacy analysis set” and “study completers.”

In the assessment of increase and decrease, the change rate within $\pm 15\%$ of the volume of ovarian chocolate cyst after treatment from before treatment initiation will be defined as “unchanged.”

If there are two or more cysts at a given assessment point, the total volume will be considered as the volume at that point and used for the analysis.

(2) Volume of ovarian chocolate cyst over time before and after treatment

For the volume calculated from the major and minor axes of ovarian chocolate cyst (a total volume if there are two or more cysts), the value, difference from the value before treatment and change rate will be calculated using the summary statistics at each measurement point and last observation in each analysis set, namely “efficacy analysis set” and “study completers,” and the Wilcoxon signed-rank test will be performed for the difference and change rate.

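### The primary cyst-volume rule has no provision for surgery, aspiration or another hormone begun during follow-up, so an on-treatment case could be counted as a decrease

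*SAP*

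**What the plan says.** SAP 6.2 defines the last observation as "The last observation of the actual evaluations after cycle 1 including those at discontinuation"; values recorded as unknown are the only exception. SAP 8.3.1 makes this the primary comparison: "the values before treatment initiation and at last observation will be compared" by sign test, in the efficacy analysis set and again in study completers. A volume change within ±15% counts as unchanged. Where a patient has several cysts, the volumes at each assessment are summed.

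Other therapies appear in two places. Protocol 4.1.2 excludes recent prior use of GnRH agonists and other hormones, and also "Subjects who received surgical treatment for endometriosis such as transvaginal alcohol fixation, laparotomy or laparoscopic surgery within 2 months before patient enrollment". Protocol 7, item (2)(viii), collects concomitant drugs and therapies during the survey, including "name of concomitant therapy, reason for implementing concomitant therapy, start date of concomitant therapy". No efficacy analysis in the SAP uses those dates.

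Two provisions limit which scans can enter. Protocol 4.5.2(5) has data entered only up to the end day of treatment when a patient discontinues. SAP 6.1 restricts study completers to patients who did not discontinue.

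**The concern.** The primary result is meant to describe what happens to cyst volume on Duphaston. If a cyst is drained, one of several cysts is removed, or another hormone is added before the scan that becomes the last observation, the volume change partly reflects that other therapy. An analyst who follows SAP 6.2 and 8.3.1 as written would still use the scan. SAP 2 describes the survey as uncontrolled, so there is no comparison group in which the same thing would happen and cancel out. At stake is the increase/decrease split on which the sign test rests.

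**Working it through.** **1. The plan's own figure.** SAP 5.3 states: "When anticipated results would be a decrease-increase ratio of 7:3 and 10% of all subjects being unchanged", and from this "a sample size is calculated to be 58 subjects". SAP 7.1 sets a two-sided 5% level. Power is not stated; I assume 80%.

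- Normal approximation for changed patients: n = (1.96 × 0.5 + 0.8416 × √(0.7 × 0.3))² / 0.2² = 46.6.
- With continuity correction: (46.6/4) × [1 + √(1 + 2/(46.6 × 0.2))]² = 51.5, rounded up to 52.
- Allowing for 10% unchanged: 52/0.9 = 57.8, rounded up to 58.
- Allowing for 10% dropout: 58/0.9 = 64.4, rounded up to 65.

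Both figures reproduce, so the sample size is not at issue. The planned split among 52 changed patients is 0.7 × 52 = 36.4, about 36 v 16.

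**2. Which scans can be affected.** Post-baseline scans are scheduled after cycle 3 and at completion or discontinuation (Protocol 7).

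| Situation | Efficacy analysis set | Study completers |
|---|---|---|
| Duphaston stopped, then procedure or switch | Later scan should not be entered (Protocol 4.5.2(5)) | Patient not included |
| Procedure or hormone on or before the end-of-treatment scan, patient discontinues | Scan used | Patient not included |
| Procedure or hormone while Duphaston continues to completion | Scan used | Scan used |

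**3. Can an affected scan cross the 15% band?** Volume is 0.52 × (mean diameter)³ (SAP 6.3).

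- Two cysts, with assumed mean diameters of 4 cm and 3 cm: 0.52 × 64 + 0.52 × 27 = 33.28 + 14.04 = 47.32 cm³. Removing the smaller one gives a fall of 14.04/47.32 = 29.7%, a decrease.
- One cyst: a 15% fall in volume needs the mean diameter to fall by 1 − 0.85^(1/3) = 5.3%, or 0.16 cm on a 3 cm cyst. Partial aspiration could do this.
- A sole cyst removed completely has no diameters to enter. It might be recorded as zero, as missing or as a comment. If it is missing, the cycle 3 scan, where there is one, becomes the last observation.

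**4. Effect on the sign test (exact, two-sided, 52 changed patients).**

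| Decrease v increase | p |
|---|---|
| 26 v 26 | 1.00 |
| 29 v 23 | 0.49 |
| 33 v 19 | 0.070 |
| 34 v 18 | 0.036 |
| 36 v 16 (planned) | 0.008 |
| 39 v 13 | 0.0004 |

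One patient moved from increase to decrease takes 33 v 19 across 0.05. Had that patient been unchanged instead, the split would be 34 v 19 of 53. That is not significant, because 35 decreases are needed among 53. Three moves from an even split, or from the planned split, leave the conclusion as it was.

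**5. False-positive chance.** Assume 58 patients, no true effect (45% decrease, 45% increase, 10% unchanged), and k patients scored as a decrease because of another therapy. The exact chance of a significant decrease, against a nominal 2.5% for that tail, is:

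| k | 0 | 1 | 2 | 3 | 4 | 5 | 6 |
|---|---|---|---|---|---|---|---|
| chance | 1.8% | 2.5% | 3.3% | 4.3% | 5.5% | 7.1% | 9.1% |

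The expected share of decreases among changed patients is (k + 0.45(58 − k)) / (k + 0.9(58 − k)): 50% at k=0, 52.9% at k=3 and 54.7% at k=5. The documents give no value for k.

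**The case against.** The strongest reply is that the plan is better protected than SAP 6.2 suggests when read alone. A reader might infer that any scan counts, including one taken after a patient stops Duphaston and has surgery or switches drug. Protocol 4.5.2(5) does not support that: entry stops at the end day of treatment. A reader might also infer that no analysis checks the result. The completers analysis removes everyone who discontinued. Both replies stand, but neither reaches a patient who has a procedure or adds a hormone while staying on Duphaston, and SAP 6.2 does not repeat the cut-off.

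A second stronger reading is that every such patient would be scored as a decrease. That does not follow either. The fall must exceed 15%, an added hormone need not achieve it, and a removed sole cyst may have no measurement at all. Nor do the documents say that these therapies are permitted during follow-up, why they were excluded beforehand, or that patients who receive them are non-responders. They are simply silent on such use, apart from a general field that records it.

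Third, using all observed scans is defensible for a survey of actual use, and setting scans aside changes what is estimated. This stands as a reason to keep the all-scans result. It is not a reason to leave the primary result open to crediting Duphaston with another therapy's effect without saying so.

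**Conclusion.** The concern holds in a limited form. As written, SAP 6.2 and 8.3.1 would use a scan affected by another cyst therapy. This applies in both analysis sets when Duphaston continues, and in the efficacy analysis set when the therapy begins on or before the end-of-treatment scan. For surgery or aspiration the likely direction is towards benefit; for an added hormone it is less certain.

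The size cannot be established. No frequency is given, and zero cases means zero effect. Under the assumptions shown, three cases would raise the chance of a false significant decrease from 1.8% to 4.3%, and five to 7.1%. A single case can matter if the split is near the threshold, whereas three would not alter the conclusion at the planned 36 v 16. The documents do not support a claim that the primary result is biased, only that the rule leaves it open to bias that the collected data could remove.

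**What to change.** In SAP 6.2 and 8.3.1:

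1. Repeat the end-of-treatment data cut-off of Protocol 4.5.2(5).
2. For cyst volume, do not use scans on or after the recorded start date of cyst surgery, aspiration or fixation, or another hormonal treatment. Take the last earlier post-baseline scan as the last observation.
3. If there is no earlier post-baseline scan, leave the patient out of the sign test and report how many there are. Add a sensitivity analysis that counts them as an increase. The category has to be named, because an unchanged patient drops out of the sign test while an increase counts against benefit.
4. Report the all-scans result alongside, and list the affected patients with the therapy and dates.

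The cost is SAP wording and a date comparison on the concomitant-therapy field, assuming that cyst procedures are entered there. The downside is a few scans set aside and a possibly less favourable split.

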6.3 Handling of Data to Derive Variables

(1) Age

If the birth date and the start date of administration are available, the age at the start date of administration will be calculated. If these dates are not available, the age entered in the EDC system will be used.

(2) Volume of ovarian chocolate cyst

The value used will be automatically calculated by the EDC system with the following conversion formula using the major axis (D1 [cm]) and minor axis (D2 [cm]) of ovarian chocolate cyst.

$$\text{Volume [cm}^3\text{]} = \{(D1 + D2) \times 1/2\}^3 \times 0.52$$

(3) Dysmenorrhea score

The dysmenorrhea score used will be a total of a dysmenorrhea severity score and a score for the use of analgesics and automatically calculated by the EDC system. If either of the scores is unknown, the dysmenorrhea score will be handled as unknown.

6.4 Handling of Adverse Event Data

Adverse event terms entered in the EDC system will be replaced with the MedDRA/J terms. The latest version of the MedDRA/J at the time of summarization will be used and clearly specified in each analysis form. If reanalysis is required, the latest version at the time of reanalysis will be used.

7 Matters concerning statistical analysis

7.1 Level of Significance for Statistical Testing and Confidence Level for Interval Estimation

Unless otherwise specified, statistical testing will be performed with a two-sided level of significance of 5%, and a two-sided confidence level of 95% will be used for interval estimation. No multiplicity adjustment will be made.

